The goal of this study is to determine whether comprehensive perioperative administration of the NMDA receptor antagonist ketamine can reduce postoperative pain tolerance and opiate consumption in chronic back pain patients undergoing spinal laminectomy/fusion when compared to saline placebo.

Investigators hypothesize that administration of a ketamine infusion intraoperatively and for 48 hours postoperatively will significantly reduce postoperative opiate consumption and VAS pain scores in chronic back pain patients undergoing spinal laminectomy/fusion when compared to those in the placebo arm.

2. * Describe the relevant prior experience and gaps in current knowledge including preliminary data. Provide for the scientific or scholarly background for, rationale for, and significance of the research based on existing literature and how it will add to existing knowledge: Patients with chronic pain are some of the most difficult to manage during the perioperative period, in part because they are often on large doses of opioids, rendering them relatively tolerant to the opioids used in the perioperative period. Several lines of evidence suggest that ketamine, administered intraoperatively, and/or post-operatively may be solution to this problem. Even more intriguingly, there is evidence to suggest that perioperative ketamine may have long term effects on opioid use. However, nearly all of the studies up to this point have investigated the short-term effects of ketamine on post-operative pain and opioid consumption. This pilot study will investigate the impact of intra-operative and post-operative ketamine on pain and opioid consumption six weeks after surgery and will support a larger NIH funded trial.

Central Sensitization and the NMDA receptor: evidence from preclinical models of pain

Seminal studies by Woolf and colleagues provided mechanistic insight into a phenomenon long appreciated by patients and clinicians alike: intense noxious stimulation results in an increase in pain from the site injury as well as from surrounding tissue well outside the injured tissue. The

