This medical record review to identify eligible candidates is minimal risk and that the rights and welfare of subjects will not be adversely affected The primary surgeon will identify patients who are prescreened via medical record to be eligible for inclusion, ask them if they would be interested in participating, and if so, the enrollment and consent process would be initiated. Participating neurosurgeons include Drs. [name], who will identify eligible patients. Informed consent will be performed by this Neurosurgeon, the PI, or other co-investigator in the study. Enrollment will be performed by the study coordinator and/or trained representative from the Acute Interventional Perioperative Pain Service (AIPPS). Enrollment will include review of eligibility, and detailed explanation of the study.

5. * Describe all compensation/incentives offered to participants and timing of these offers:

Participants will be compensated up to \$100 for travel and parking expenses related to Pre-Op Visit (\$50) and 6-Week Follow-up visit (\$50)

Recruitment materials: (attach all material to be seen or heard by subjects, including advertisements and scripts)

Document Category Date Modified Document History

There are no items to display

View: Pitt SF: Study Design

Study Design

1. Total number of subjects to be enrolled at this site (enter -1 for chart reviews, banking, registries):
20

2. Describe and explain the study design:

This study is being proposed as a pilot study to inform the feasibility and direction of a larger P01 NIH funded trial.

3. Describe the primary and secondary study endpoints:

Primary Outcome measure:

- ¬ Pre- and post-surgical pain rating
- \neg Pre- and post-surgical opioid utilization (in morphine equivalent units in the PACU and post-operative period until discharge, at 14 days, and at 6 weeks follow-up)
- ¬ Pre- and post-surgical opioid analgesic efficacy

Secondary outcome measures:

- ¬ Mcgill Pain Questionnaire-Short Form
- ¬ Pain Catastrophizing Scale
- ¬ PROMIS Emotional Distress-Anxiety Short Form
- ¬ PROMIS Emotional Distress-Depression Short Form
- ¬ Neuro-QoL Short Form v1.1 Satisfaction with Social Roles and Activities
- ¬ Cold Pressor Test

4. Provide a description of the following study timelines:

Duration of an individual subject's active participation:

6 weeks

Duration anticipated to enroll all subjects:

5 months

Estimated date for the investigator to complete this study (complete primary analyses):

10/31/2019

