5. List the inclusion criteria:

Patients undergoing lumbar spine surgery of at least one level, and no more than 4 levels.

Patients with chronic back pain (>3 months)

ASA 1-3

Age 18-65

Opiate-dependent, meeting both of the following criteria:

- 1.Daily opiate use for at least 2 months
- 2. Oral morphine equivalent of 60 mg/day or higher

- 6. List the exclusion criteria:
 - -Intolerance or known allergy to ketamine
 - -History of increased intraocular pressure (> 22mmHg)
 - -Uncontrolled hypertension (systolic blood pressure greater than or equal to 180, diastolic blood pressure greater than equal to 100)
 - -Increased intracranial pressure (signs including:Behavior changes, Decreased consciousness, Headache, Letharqy
 - -Neurological symptoms, including weakness, numbness, eye movement problems, and double vision, seizures, vomiting)
 History of psychosis

Pregnancy

Patients with significant liver disease (signs and symptoms of liver injury, such as discolored skin and eyes that appear yellowish, abdominal pain and swelling, Itchy skin that doesn't seem to go away, Dark urine color, Pale stool color, Bloody or tar-colored stool, Chronic fatigue, Nausea, Loss of appetite, with or without elevated LFTs: AST > 120 IU/ml, AP >130 IU/ml, and ALT >40 IU/ml)

- -Patients with exposure to CYP3A and / or CYP2B6 inhibitors, including the herbs and the over-the-counter compounds (list of drugs can be found at http://www.fda.gov/drugs/developmentapprovalprocess/developmentresources/druginteractionslabeling/ucm093664.htm)
- 7. Will children or any gender, racial or ethnic subgroups be explicitly excluded from participation?
 - Yes No
 - * Identify the subgroups and provide a justification: Presbyterian Hospital is an adult-only facility
- 8. Describe the power analysis used and cite your method of statistical analysis. If a power analysis is not possible, thoroughly justify the sample size required for the study, including appropriate literature citation (alternatively provide page reference in attached protocol):

 This is a pilot to support a P01 program pilot application to the NIH, so the data will be analyzed mainly using descriptive statistics. Additional statistical analysis methods such as a 2-sample t test to compare significance between groups may also occur.

View: Pitt SF: Research Activities

Research Activities

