The subject will be asked to come into the [name] on a date after the clinic visit but before their day of surgery for a Pre-Operative Visit. Investigators will work with the subject to determine their opioid dose regimen, and the subject will be asked to come into the Aiken Medical Building thirty minutes before their opioid dose is due and will be asked to bring with them their upcoming dose of pain medication. Prior to taking their pain medication, the subject will then be administered a coldpressor pain sensitivity test. For this test, the subject will place their nondominant hand in a bowl of ice water up to the wrist. Pain threshold is defined as the time in seconds that is takes for the subject to first report the sensation of pain in the immersed hand. Pain tolerance is defined as the time in seconds that it takes for the subject to withdraw their hand from the ice water because it has become too uncomfortable for them to keep their hand immersed any longer. A cut-off of four minutes will be imposed to limit the potential for any tissue damage. At this time, the subject will be asked to remove their hand from the ice water, even if they say that they could keep their hand immersed for longer. Pain threshold, tolerance and cut-off will be recorded using a stop watch. Heart rate and blood pressure

will be recorded before and after the cold-pressor test. Once the cold pressor test is completed, the McGill Pain Questionnaire will be administered. After this questionnaire is complete, the subject will take the dose of opioid medication they have brought from home and are scheduled to receive and will wait in the clinic for 30 minutes for the pain medication to take effect. Once the 30 minutes is complete, the cold-pressor test will be repeated, heart rate and blood pressure collected before and after, and McGill Pain Questionnaire will be administered again. Opioid-analgesic efficacy will be estimated by the change in pain threshold and tolerance observed after the opioid was consumed relative to initial assessment of pain threshold and tolerance. The subject will be compensated \$50 for this pre-operative visit.

Surgical Visit:

Study groups:

Patients will be randomized to one of the following groups:

- 1. Intraoperative ketamine- post operative 48 hr ketamine infusion
- 2. Intraoperative placebo (saline)- post operative placebo (saline) infusion

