Randomization will occur by a computer based system at a 1:1 ratio. The Investigational Drug Pharmacy will create the randomization log and IDS will randomize the subject independent of the research team. The study drug/placebo will look identical to maintain the blind for all clinicians and research staff involved.

At the day of surgery, subjects will be seen by team members of the Acute Interventional Perioperative Pain Service preoperatively. Pregnancy will be assessed via medical record, as it is standard of care for these patients to take a pregnancy test day of surgery. Since the ketamine infusion will occur for 48 hours while patient is in the hospital, there is little risk of becoming pregnant during study drug treatment period

Enrolled participants will receive a 1 mg/kg dose of intravenous ketamine or saline 15 minutes after induction of general anesthesia. Thereafter, a continuous infusion of 0.20 mg/kg/hr ketamine or saline with a maximum dose of 20 mg/hr will be run to conclude at 48 hours after the end of the surgery (fascial closure).

A standardized general anesthesia protocol will be used by the hands-on provider. All drugs used intraoperatively, including total hydromorphone dose, will be collected from the electronic medical record.

The amount of narcotics and non-narcotic analgesics administered in the operative and postoperative period will be collected from the electronic chart from day of surgery until discharge. VAS pain scores will be collected

from the PACU until discharge from the hospital.

Pain will be monitored every four hours, except during the night when the participant is asleep. We will use a scale from 0-10, 0 being no pain, 5 being moderate pain and 10 being the worst imaginable pain. The participant will also be asked to score pain at its best and worst over the period since they were last asked.

Post-Op Visit: Approximately 1 hour

Patients will follow-up at Neurosurgery clinic at 10-14 days postoperatively. At this time daily opioid usage will be assessed and converted to morphine equivalents/24 hr. At this visit, the McGill Pain questionnaire-Short form, pain medication review form, and the Pain Catastrophizing Scale (PCS) (Sullivan, 1995). PROMIS Emotional Distress-Anxiety Short Form and PROMIS Emotional Distress-Depression Short Form, Brief Psychiatric Rating Scale and Neuro-QoL Short Form v1.1 - Satisfaction with Social Roles and Activities will also be completed by the participant.

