STUDY: Perioperative Ketamine in Opioid-Tolerant Patients Undergoing Lumbar Spine Surgery: A

Randomized, Double-blind, Place-controlled Trial

Principal Investigator: [name], PhD, MBA

IRB: STUDY19020144

NCT: 04220489

Statistical Analysis Plan – Approved 09/03/2019

This is a pilot to support a P01 program pilot application to the NIH, so the data will be analyzed mainly using descriptive statistics. Additional statistical analysis methods such as a 2-sample t test to compare significance between groups may also occur.

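### Preoperative opioid dose is recorded, but no balancing of it in the 20-patient allocation is described and the planned comparison does not adjust for it

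*Protocol*

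**What the plan says.** **Allocation.** Research Activities item 1 (Surgical Visit) says that "Patients will be randomized to one of the following groups", names a ketamine and a placebo group, and adds that "Randomization will occur by a computer based system at a 1:1 ratio". On who builds the list: "The Investigational Drug Pharmacy will create the randomization log and IDS will randomize the subject independent of the research team". How the log is built (blocks, strata, minimisation) is not described.

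**Size.** Study Design item 1 gives 20 for "Total number of subjects to be enrolled at this site". No power or precision argument accompanies it.

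**Entry.** Study Design item 5 admits "Patients undergoing lumbar spine surgery of at least one level, and no more than 4 levels" and requires "Oral morphine equivalent of 60 mg/day or higher", which is a floor without a ceiling.

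**Link to outcome.** Study Aims item 2 says of chronic pain patients that "they are often on large doses of opioids, rendering them relatively tolerant to the opioids used in the perioperative period". Postoperative opioid use is the primary outcome in Basic Information item 3 and one of three primary outcomes in Study Design item 3.

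**Baseline data.** A pain medication review form is completed at the Screening Visit, and the opioid regimen is established for the Pre-Operative Visit.

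**Analysis.** In the SAP, "the data will be analyzed mainly using descriptive statistics". A two-sample t test is optional. Neither document names a covariate.

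**The concern.** On the Protocol's own reasoning, patients who take more opioid before surgery should need more after it. If the ketamine arm happens to receive the lower-dose patients, its postoperative use will tend to be lower with no drug effect. The reverse imbalance would hide a real effect. With about 10 per arm such imbalances are common, and a simple summary by arm or an unadjusted t test takes no account of them.

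This matters because the pilot is meant to inform both the feasibility and the direction of a larger trial, and Study Aims item 1 states a hypothesis of reduced opioid use and pain. The opioid figures by arm are therefore likely to be read as a signal.

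**Working it through.** The plan has no figure of its own to reproduce, since N = 20 comes without inputs.

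**Inputs from the documents:** 20 patients at 1:1, so 10 per arm if the split is even. The 30% yardstick is the lower end of the 30–50% reduction in rescue analgesics quoted in Study Aims item 2.

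**Assumed inputs (the documents give none):** log dose and log opioid use roughly normal; correlation r between them 0.3 to 0.7; SD of log opioid use s 0.4 to 0.8. The central case is r = 0.5, s = 0.6.

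**1. Chance imbalance in preoperative dose.** The difference in arm means, in SD units, has standard error √(2/10) = 0.447.
- Beyond 0.5 SD: 2 × [1 − Φ(0.5/0.447)] = 26%.
- Beyond 0.8 SD: 2 × [1 − Φ(0.8/0.447)] = 7.4%.
- 95% range: ±1.96 × 0.447 = ±0.88 SD.

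**2. What an imbalance does to the opioid comparison.** An imbalance of 0.5 SD shifts the geometric mean by 1 − exp(−0.5 × r × s).
- Central case: 1 − exp(−0.15) = 13.9%.
- Range: 5.8% (r = 0.3, s = 0.4) to 24.4% (r = 0.7, s = 0.8).

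**3. The t test.** In simulation under no drug effect, the unadjusted test on log use keeps its 5% two-sided error over all trials. Among trials with an imbalance of at least 0.5 SD favouring ketamine, the false-positive rate in that direction is about 6%, 9% and 13% at r = 0.3, 0.5 and 0.7, against 2.5% nominally.

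**4. Imbalance with a stratified list.** With two strata cut at the median dose and permuted blocks of 2 and 4, simulation gives an SD of the baseline difference of about 0.288. Differences beyond 0.5 SD fall from 26% to 8%, and beyond 0.8 SD from 7% to 0.6%. A poorly placed cut does less: beyond 0.5 SD becomes 12%, 11% and 17% for cuts at the 25th, 70th and 85th percentiles. The arms end up unequal in about 35% of trials.

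**5. The quantity that matters.** This is the chance, with no drug effect, that ketamine shows at least 30% lower geometric mean opioid use. In the central case, ln 0.7 = −0.357.
- As planned (10:10): SD = 0.6 × 0.447 = 0.268; Φ(−0.357/0.268) = 9.2%.
- Stratified list only: variance = 0.36 × (0.25 × 0.288² + 0.75 × 0.2) = 0.0615, SD 0.248; Φ(−0.357/0.248) = 7.5%.
- Adjustment for log dose only: variance = 0.36 × 0.75 × (0.2 + 0.2/16) = 0.0574, SD 0.240; Φ(−0.357/0.240) = 6.8%. The term 0.2/16 is the cost of estimating the slope.

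Simulation agrees: 9.0–9.2%, 7.2–7.6% and 6.7%. With both measures it gives 6.4%.

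| r (s = 0.6) | As planned | Stratified only | Adjusted only |
|---|---|---|---|
| 0.3 | 9.1% | 8.5% | 8.7% |
| 0.5 | 9.1% | 7.5% | 6.7% |
| 0.7 | 9.1% | 5.8% | 3.5% |

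The fall in step 4 (26% to 8%) is therefore much larger than the fall in false signals (about 9% to 7.5%), because most of the variation in opioid use is unrelated to preoperative dose.

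**The case against.** The strongest case against is that this is a 20-patient pilot with mainly descriptive aims, where omitting stratification is common and defensible. Randomisation protects against systematic bias, the t test keeps its overall error rate, and the remedy moves the false-signal rate by only about two percentage points in the central case. The endpoint section also lists pre- and post-surgical opioid use together, so baseline dose may well be visible beside the outcome. Much of this stands, and it limits the size of the point. It does not remove it: no change score, adjustment or baseline table is specified, and the documents give the pilot a role in setting direction.

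Four stronger readings are tempting but not supported:
- *The trial is unstratified or unblocked.* The documents are silent on how the pharmacy builds the log. A split of 7:13 or worse would occur in 26% of trials under unblocked assignment, but no section says the list is unblocked.
- *The allocation is biased.* It is not. The concern is how a single imbalanced realisation would be read.
- *Preoperative doses are known to differ widely and to be the main driver of opioid need.* The documents give a floor and a qualitative link, with no SD and no correlation.
- *Stratification would cure the problem.* It removes part of it, and at r = 0.5 or above it does less than covariate adjustment.

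The 30% yardstick is also weak here, since Study Aims item 2 says that most of the reviewed studies enrolled patients without prior chronic pain.

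**Conclusion.** The point holds in a limited form. The plan records preoperative dose and gives a reason to think it prognostic, yet describes no use of it in allocation or analysis. The 26% chance of an imbalance beyond 0.5 SD needs only 10 per arm and approximate normality of log dose. The effect on false signals (about 9% to 7.5% or 6.7%) rests on the assumed r and s: it nearly vanishes at r = 0.3 and is substantial at r = 0.7. Adjustment is the stronger part of the remedy across the middle and upper range of r. Neither measure changes the main limitation, which is the sample size.

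**What to change.** 1. **SAP.** State that any between-arm comparison of postoperative opioid use is made on the log scale with log preoperative morphine-equivalent dose as a continuous covariate. Report preoperative dose and number of surgical levels by arm beside the raw summaries. Cost: one degree of freedom and two table rows.

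2. **Research Activities item 1 (Surgical Visit).** State that the pharmacy builds a concealed permuted-block list, with block sizes 2 and 4 randomly mixed, within two strata of preoperative dose, the cut being fixed before the first patient. Use dose as the only factor, because two binary factors would leave about 20/4 = 5 patients per cell. If the existing log is already blocked or stratified, describe it. Cost: a protocol amendment and passing a dose band to the pharmacy; slightly more predictable small blocks, limited by the mixed sizes and pharmacy-held list; and arms not exactly 10:10 in about 35% of trials. This part must be in place before allocation starts.

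3. **Before defining strata,** reconcile the definitions of opioid dependence. Basic Information item 3 has more than 60 mg/day for more than one week. Study Design item 5 has 60 mg/day or higher with daily use for at least 2 months.

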STUDY: Perioperative Ketamine in Opioid-Tolerant Patients Undergoing Lumbar Spine Surgery: A

Randomized, Double-blind, Place-controlled Trial

Principal Investigator: [name], PhD, MBA

IRB: STUDY19020144

NCT: 04220489

Study Protocol – Approved 09/03/2019

Basic Information

1. * Title of study:

Perioperative Ketamine in Opioid-Tolerant Patients Undergoing Lumbar Spine Surgery: A Randomized, double-blind, placebo-controlled trial

2. * Short title:

Perioperative Ketamine in Opioid-Tolerant Patients Undergoing Lumbar Spine Surgery

3. * Brief description:

The goal of this study is to determine whether comprehensive perioperative administration of the NMDA receptor antagonist ketamine can increase postoperative pain tolerance and reduce opiate consumption in chronic back pain patients undergoing spinal laminectomy/fusion when compared to placebo

Design: Prospective, Randomized, Double-Blind, Placebo Controlled trial involving opiate-dependent patients undergoing lumbar spine surgery. Opioid dependence will be defined as greater than 60 mg oral morphine equivalents/day for greater than one week. Intraoperatively, patients will receive a 1 mg/kg dose of intravenous ketamine or saline with 15 minutes after induction of general anesthesia. Thereafter, a continuous infusion of 0.20 mg/kg/hr ketamine with a maximum dose of 20 mg/hr or saline will be run to conclude at 48 hours after the end of the surgery (fascial closure). The primary outcome measure will be hydromorphone PCA usage during the first 72 hours postoperatively. Secondary outcome measures will be VAS pain scores at rest and with movement in PACU, 24 hr, 48 hr, 72 hr, 2 week (post-op visit), 6 week follow-up visit, as well as, McGill Pain Questionnaire, Pain Catastrophizing Scale, and emotional distress surveys assessing depression and anxiety at preop/screening, postop and 6 week follow-up (PROMIS Emotional Distress-Anxiety Short Form, PROMIS Emotional Distress-Depression Short Form), as well as a Neuro-QOL Short Form v1.1 - Satisfaction with Social Roles and Activities.

4.	* Principal investigator:
	[name]

5 .	*	Does	the	investigator	have a	financial	interest	related	to this	researd	:h?
	- 0	Ye	s 💿	No							

6. * Will an external IRB act as the IRB of record for this study?

O Yes No

- 7. * What kind of study is this? Single-site study
- 8. Attach the protocol:
 - Sponsor/Multicenter protocol
 - Investigator-initiated protocol
 - Emergency Use Consent/ Protocol/ FDA Form 3926

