6-Week Follow-Up Visit: Approximately 1.5 hours

The subject will be asked to come to the [name] approximately 6 weeks after their surgery for a 6-Week Follow-Up Visit. Investigators will work with the subject to determine their post-operative opioid dose regimen, and the subject will be asked to come in for the visit thirty minutes before their opioid dose is due and bring with them their upcoming dose of pain medication. Prior to taking their pain medication, the subject will then be administered a cold-pressor pain sensitivity test, in a manner identical to that use during the pre-operative assessment.In addition to the McGill Pain Questionnaire-Short form, a pain medication review form, the Pain Catastrophizing Scale (PCS) (Sullivan, 1995), the PROMIS Emotional Distress-Anxiety Short Form, the PROMIS Emotional Distress-Depression Short Form, Brief Psychiatric Rating Scale and Neuro-QoL Short Form v1.1 - Satisfaction with Social Roles and Activities will also be completed. The subject will be compensated \$50 for this 6-week follow-up visit.

Upload a copy of all materials used to collect data about subjects: (Attach all surveys, interview/focus group scripts, and data collection forms except for case report forms, SCID or KSADS):

	Document	Category	Date Modified	Document History
View	Brief Psychiatric Rating Scale (0.01)	Data Collection	3/6/2019	History
View	PROMIS v1.0 ED-Depression Short Form 1.pdf(0.01)	Data Collection	3/6/2019	History
View	PROMIS v1.0 ED-Anxiety Short Form 1.pdf(0.01)	Data Collection	3/6/2019	History
View	Pain%20catastrophizing%20scale-1.docx(0.01)	Data Collection	3/6/2019	History
View	Neuro-QOLv1.1- SatisfactionwithSocialRolesandActivitiesSF 03-06- 2014.pdf(0.01)	Data Collection	3/6/2019	History
View	Medications- questionaire.doc(0.01)	Data Collection	3/6/2019	History
View	Mcgill pain questionaire.docx(0.01)	Data Collection	3/6/2019	History

3. * Will blood samples be obtained for research purposes?

○ Yes [©] No

View: Pitt SF: Consent Process

Consent Process

Enter N/A in response to the following questions if a Waiver of Consent is requested for all research activities or if no subjects are being enrolled.

1. * Indicate where the consent process will take place and at what point consent will be obtained:

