2.

Refer to the following templates and instructional documents:

- Guidance Consent Wording
- Template Consent Document Short Form
- HRP-090 SOP Informed Consent Process for Research
- HRP-091 SOP Written Documentation of Consent

View: Pitt SF: Medical Records

Medical Records

1. You are required to submit this study to the Research Informatics Office, Health Record Research Request (R3). Per UPMC Policy HS-RS0005, all research projects that access or involve UPMC electronic protected health information (e-PHI) must be submitted to R3, with the exception of clinical trials that are contracted through the UPMC Office of Sponsored Programs and Research Support (OSPARS).

Complete the R3 intake form available at http://rio.pitt.edu/services. An R3 representative will conduct a review. You will be notified once your R3 review is complete or if anything further is needed.

* Describe the protected health information that will be collected from the covered entity and/or the research derived information that will be placed into the medical records:

Patient demographics and medical history will be collected from the medical record

The amount of narcotics and non-narcotic analgesics administered in the operative and postoperative period will be collected from the electronic chart from day of surgery until discharge. VAS pain scores will be collected from the PACU until discharge from the hospital.

View: Pitt SF: Electronic Data Management

Electronic Data Management

1. * Will only anonymous data be collected (select NO if identifiers will be recorded at anytime during the conduct of the study)?

° Yes [®] No

Select all identifiers to be collected during any phase of the research including screening:

E-mail address: Social security #: Phone/Fax #: Account #: Medical record #:	Web Unit Social se Full face images: Health pl Device ic	Protocol (IP) Address: versal Resource Locators (URLs): ecurity # (for Vincent payment only): photo images or comparable an beneficiary #: lentifiers/serial numbers: dentifiers/serial #/license plate #: c identifiers, finger and voice	
a: Will you be collect the following locating geographic subdiving than a State such a address, city, countainty geocodes, etc. b: Will you be collected: b: Will you be collected: b: Will you be collected:	on data: isions smaller is street ty, precinct, ? cting any date s birth date, discharge, vice? hique s, codes related	Yes ○ NoYes ○ No	

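### VAS at rest and with movement is listed at six times, but the visit procedures never ask for either condition and name no VAS at 2 or 6 weeks

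*Protocol*

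**What the plan says.** The outcome list in the Protocol's brief description (Basic Information, item 3) gives as a secondary outcome "VAS pain scores at rest and with movement in PACU, 24 hr, 48 hr, 72 hr, 2 week (post-op visit), 6 week", the last being the follow-up visit.

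The procedures read differently:

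- **Ward, VAS.** Medical Records states: "VAS pain scores will be collected from the PACU until discharge from the hospital". Research Activities, item 1 (Surgical Visit) says the same.
- **Ward, 0-10 score.** The Surgical Visit text goes on: "Pain will be monitored every four hours, except during the night when the participant is asleep". The scale follows: "We will use a scale from 0-10, 0 being no pain, 5 being moderate pain and 10 being the worst imaginable pain". Then: "The participant will also be asked to score pain at its best and worst over the period since they were last asked". Nothing says whether this rating is the VAS or a second measure.
- **10-14 day visit.** The list of instruments opens "At this visit, the McGill Pain questionnaire-Short form, pain medication review form, and the Pain Catastrophizing Scale (PCS" and continues with the PROMIS, psychiatric rating and Neuro-QoL forms.
- **6-week visit.** After the cold pressor test the list opens "In addition to the McGill Pain Questionnaire-Short form, a pain medication review form, the Pain Catastrophizing Scale (PCS" and continues in the same way.

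Neither visit list contains a VAS or a 0-10 score. The form's own instruction for this section asks for a complete description of the research activities, screening and follow-up included.

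Elsewhere, the hypothesis in Study Aims, item 1 names VAS without a condition or a time point. Study Design, item 3 makes a pain rating before and after surgery a primary outcome without naming its scale, and its secondary list has no VAS. The SAP defines no pain variable.

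**The concern.** Coordinators work from the visit text. It lists the follow-up instruments one by one, so an instrument that is not on the list is likely not to be given. A pain score that is not asked for at a visit cannot be reconstructed afterwards.

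Two parts of a listed secondary outcome are exposed. One is the rest/movement split, which no procedure requests at any time. The other is VAS at 2 and 6 weeks. Best and worst since the last assessment do not stand in for rest and movement, because the worst pain in an interval may have occurred at rest. The follow-up gap matters to this pilot in particular: Study Aims says that most earlier work looked at short-term effects and that this study will look at pain six weeks after surgery.

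**Working it through.** No sample-size or power figure is involved. The check sets the outcome list against the procedures and counts.

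| Time in the brief description | VAS or 0-10 score in the procedures | Rest or movement stated |
|---|---|---|
| PACU | yes | no |
| 24 h | yes, from ward scoring | no |
| 48 h | yes, from ward scoring | no |
| 72 h | only if still in hospital | no |
| 2 weeks (10-14 day visit) | none named; McGill named | no |
| 6 weeks | none named; McGill named | no |

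The first three times fall within the inpatient infusion: "Since the ketamine infusion will occur for 48 hours while patient is in the hospital". No text requires a stay to 72 h. The brief description counts PCA use to 72 h, which fits such a stay but does not guarantee it. No rule says which four-hourly reading serves as the 24, 48 or 72 h value.

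**Values intended.** 6 times × 2 conditions = 12 per patient.

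**Condition specified in the procedures.** 0 of 6 times, so 0 of 12 values.

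**Follow-up values at risk.** 2 visits × 2 conditions = 4 per patient. With the planned 20 patients (Study Design, item 1), 4 × 20 = 80. The loss depends on forms that are not shown:

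- no form holds a VAS item: 80 lost;
- one item without a condition at each visit: 2 × 20 = 40 scores exist. If each is accepted as one of the pair, 80 − 40 = 40 are lost. If the condition must be known, none of the 80 is obtained as specified;
- both conditions asked at each visit: 0 lost.

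**Ward values.** 4 times × 2 conditions = 8 per patient. If the VAS and the 0-10 rating are one measure, one current score per time fills at most 4 of 8, or 3 of 8 for a patient discharged before 72 h. Those scores would still carry no condition.

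**Before surgery.** McGill is named at four clinic visits (screening, pre-operative, 10-14 day, 6-week) and at no ward time. VAS or 0-10 is named on the ward and at no pre-operative visit. As written, the ward scores have no named pre-operative value on the same scale.

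**The case against.** The strongest reply is that the documents leave something out rather than rule something out. The Medical Records section answers a question about chart data, which for an inpatient naturally ends at discharge, and the matching Surgical Visit sentence directly follows one about the electronic chart. Neither says that VAS stops there, and the brief description itself assigns VAS to the 2- and 6-week visits. This stands. A reader might infer that the protocol limits VAS to the hospital stay, but the text does not support that.

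Second, the uploaded McGill form and the case report forms are not shown, and either could hold a VAS item. This also stands, and it is why the loss is given as a range. None of the seven uploaded forms is titled as a VAS, but the upload request exempts case report forms, so that is weak evidence.

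Third, McGill measures pain at both follow-up visits, and the hypothesis asks for neither a rest/movement split nor a six-week VAS. A reader might infer that the trial has no six-week pain data or cannot address its hypothesis. Both inferences go too far.

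Fourth, the brief description promises no pre-operative VAS, and a randomised comparison of ward scores does not need one. This is correct. A pre-operative score is a useful addition, not a missed commitment, and the unnamed scale of the primary pain rating is a neighbouring issue.

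Fifth, this is a 20-patient pilot analysed mainly by description. That lowers the stakes but does not remove the point, since a descriptive summary still needs the scores to have been asked for.

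**Conclusion.** The point holds as a mismatch between a listed outcome and the procedures meant to collect it. The rest/movement condition is absent from the procedures at all 6 listed times, and 2 of the 6 times have no VAS or 0-10 score in their visit lists. The 72 h score is conditional on the hospital stay and should not be counted as lost.

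The loss at follow-up lies between 0 and 80 values in 20 patients. The upper figure assumes that staff follow the visit text and that no unseen form carries the item, so it should not be quoted as an established loss. Confidence is medium for that reason. The change is worth making because the omission cannot be repaired afterwards and costs little to prevent.

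**What to change.** Reconcile the brief description, the endpoint list in Study Design, the visit text in Research Activities and the Medical Records section.

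1. State whether the VAS and the four-hourly 0-10 rating are one measure. Settle this first, because the added questions must use the measure that the outcome names.
2. Add that measure, asked once at rest and once with movement, to the 10-14 day and 6-week visit lists and to the PACU, 24, 48 and 72 h assessments. Do not simply relabel the existing single score. Report 72 h as not obtained if the patient has left hospital.
3. As a cheap addition, ask the same pair once at the existing screening or pre-operative visit, and name the scale of the primary pain rating in Study Design. The ward scores then have a pre-operative value on their own scale.
4. If the rest/movement split or the follow-up VAS is not intended, remove it from the brief description instead.

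Cost of steps 2 and 3: 2 questions × 3 clinic visits = 6. On the ward, add 1 × 4 = 4 if the existing score becomes one of the pair, or 2 × 4 = 8 if both are new. The total is 10 or 14 short questions per patient, at most 200 or 280 in 20 patients, all at existing contacts, plus an IRB wording change. Step 4 costs only the wording change.
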